### 8.1.2. Primary Efficacy- Sensitivity Analysis

The following sensitivity analyses will be performed to assess the robustness of the results of the primary analyses and to test the assumptions of the MMRM model:

[figure not shown]
- The primary efficacy analyses will be repeated using the PP Population.

- The primary efficacy analyses will be repeated using the mITT Population.
- The treatment effect will be pooled across Stages 1 and 2 using 0.5/0.5 weighting for Stage 1/Stage 2.

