## **3. Overall Study Design and Plan**

### **3.1. Overall Design**

### **3.2. Sample Size and Power**

Response to treatment will be measured using the CAPS-5 score change from baseline to Week 4 (Stage 1) and from Week 4 to Week 8 (Stage 2). If the effect size of NYX-783 is in line with the effect sizes observed in similar historical studies, this study is powered at approximately 80% to reject the null hypothesis at a one-sided  $\alpha = 0.10$  level for any single specified efficacy comparison. The sample size estimate (n=156) assumes a 15% dropout during Stage 1 and 11% dropout during Stage 2, based on the treatment comparisons specified for [Amendment 2](#) of the protocol. The sample size may be adjusted if the actual dropout rate exceeds this assumption; patients randomized based on earlier protocol versions will be included in data listings, but will not be included in data summaries or inferential analyses.

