- **Per-Protocol Population (PP):** The PP Population will consist of all ITT Population subjects who do not incur a major protocol violation that would challenge the validity of their data (including compliance assessment). This population will be used to evaluate the sensitivity of the primary efficacy analysis. For the same reason as ITT population, a PP Stage 1 population (subjects from ITT without any major protocol deviation) and a PP Stage 2 population (subjects from ITT without any major protocol deviation entering Stage 2) will be created.

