#### 6.1.3. Handling of Dropouts or Missing Data

Missing efficacy data will be handled using MMRM's maximum likelihood method. No additional imputation is planned to be performed.

In general, there will be no substitutions made to accommodate missing data points. All data recorded on the case report form (CRF) will be included in data listings that will accompany the clinical study report.

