### 6.1.4. Derived Variables

- Actual treatment received: After unblinding, all blister cards dispensed will be unblinded. Actual treatment will be defined by stage as the higher dose received at least one time (one capsule) during the corresponding stage (50mg > 10mg > Placebo).
- CAPS-5 (Clinician Administered PTSD Scale for DSM-5) = The CAPS-5 is a 30-item structured interview for diagnosis and assessment of PTSD. CAPS-5 scores are derived at data-management level. CAPS-5 total symptom severity score is calculated by summing severity scores for the 20 DSM-5 PTSD symptoms. Similarly, CAPS-5 symptom cluster severity scores (subscores) are calculated by summing the individual item severity scores for symptoms corresponding to a given DSM-5 cluster: Criterion B, intrusions (items 1-5); Criterion C, avoidance (items 6-7); Criterion D, negative alterations in cognitions and mood (items 8-14); and, Criterion E, alterations in arousal and reactivity (items 15-20). The assessor combines information on frequency and intensity of an item into a single severity rating (0-4) for each of the 20 DSM-5 PTSD symptoms, with a maximum possible score of 80 points. A higher score corresponds to more severe PTSD.
- PCL-5 (PTSD Checklist for DSM-5) = The PCL-5 is a 20-item self-report measure that assesses PTSD symptoms experienced over the last week or month according to DSM-5 criteria. PCL-5 score is derived at data-management level. Items assess symptoms across 4 symptom clusters of PTSD (re-experiencing, negative mood, avoidance, and hyperarousal) on a 0-4 point Likert scale. Total scores range from 0-80. The “since last week” version should be used after screening. A higher score corresponds to more severe PTSD. PCL-5 response is defined as decrease (from baseline) of 10 points at the end of each stage (week 4/week 8) [6]. If total score is missing at one time point (Week4/Week8) then response will be set to missing. If patient early terminated and assessment at Week 4 or Week 8 missing then patient will be a non-responder. Baseline defined as in section 6.1.1.

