#### 8.1.1. CAPS-5

The primary efficacy endpoint is change in CAPS-5 total score and subscores following 4 weeks of treatment in each respective Stage (Stage 1 [baseline to Week 4] and Stage 2 [Week 4 to Week 8]). Changes from baseline for specific visits and treatment groups will be used for the comparison of NYX-783 to placebo as described in Section 6 (for specification of visit alignment) and Section 6.1.1 (for information on baseline derivations). Modeled data will consist of change from baseline data through Week 4 for all of those randomized to treatment arms 1, 2 or 3 for Stage 1; and change from Week 4 assessment data for subjects randomized to arms 7, 8, or 9 for Stage 2.

The primary efficacy endpoint will be evaluated using the weighted combination of the estimated treatment effects from the Stage-specific mixed models for repeated measures (MMRM). The MMRM models will include variables for treatment group, visit, treatment-by-visit interaction term, baseline CAPS-5 score as covariate, and baseline-by-visit interaction. An unstructured covariance matrix will be used. If the model fails to converge with an unstructured covariance matrix other structures will be tried and the structure with the lowest corrected Akaike information criterion (AICC) will be used for the analysis. Full details will be included in the CSR. The Kenward-Roger approximation will be used to adjust the denominator degrees of freedom.

The treatment effect will be assessed as the differences in least-squares mean (LS mean) changes from baseline to Week 4 (Stage 1) and from Week 4 to Week 8 (Stage 2) for the NYX-783 50 mg QD, NYX-783 10 mg QD, and placebo groups defined in Section 8.1. A pairwise comparison will be made between each of the NYX-783 arms and placebo. The treatment effect will be pooled across Stages 1 and 2 using pre-specified 0.6/0.4 weighting for Stage 1/Stage 2.

Combined inference is computed using the weighted linear combination of stage-wise test statistics:

$$Z_{Combined} = \frac{0.6\widehat{\delta}_1 + 0.4\widehat{\delta}_2}{\sqrt{0.6^2Var(\widehat{\delta}_1) + 0.4^2Var(\widehat{\delta}_2)}}$$

Where,  $\widehat{\delta}_1$  is the estimated Stage 1 treatment effect and  $\widehat{\delta}_2$  is the estimated Stage 2 treatment effect. The combined test statistic  $Z_{combined}$  is used to compute the overall one sided treatment effect p-value.

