## 10. Other Planned Analysis

## 10.2. COVID-19 Assessment Impact

To address the impact of COVID-19 on evaluating the efficacy of the trial, the following approach will be implemented:

- First describing the population : randomized date, visits missed, visits done remotely, restriction due to COVID-19 by visit. Restriction due to COVID-19 is defined as first day to stay at home, it will be defined by state.
- Second a sensitivity analysis on efficacy endpoints CAPS-5, PCL-5, PSQI score, HADS will be run. The main MMRM model will be run adding the COVID-19 restriction variable to evaluate impact of this covariate on treatment difference estimates. This covariate will be a time-varying covariate.
- A listing of all patient impacted by COVID-19 will be produced.

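### SAP 8.1.2 says its sensitivity analyses test the MMRM assumptions, but none in the available text does so for CAPS-5; separately, the PP Stage 1 wording lets a Stage 2-only deviation remove Stage 1 data

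*SAP*

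**What the plan says.** - **Stated purpose.** SAP 8.1.2 says its analyses are "to assess the robustness of the results of the primary analyses and to test the assumptions of the MMRM model". It does not name the assumptions. Three analyses follow: the primary analysis on the PP set, the same on the mITT set, and stage weights of 0.5/0.5 in place of 0.6/0.4.
- **Missing data.** SAP 6.1.3 relies on the MMRM likelihood and adds: "No additional imputation is planned to be performed". Protocol 14.4.2 leaves any other supporting missing-data analysis to the SAP.
- **COVID-19.** SAP 10.2 covers CAPS-5: "The main MMRM model will be run adding the COVID-19 restriction variable".
- **Covariance.** SAP 8.1.1 specifies an unstructured matrix. "If the model fails to converge with an unstructured covariance matrix other structures will be tried". The pseudo-code has `type=un` and no `group=` option, so one matrix serves all arms.
- **PCL-5 response.** SAP 6.1.4 has a different rule: "If patient early terminated and assessment at Week 4 or Week 8 missing then patient will be a non-responder". It applies to a binary secondary measure, not to CAPS-5.
- **Dropout.** The sample size estimate "assumes a 15% dropout during Stage 1 and 11% dropout during Stage 2" (SAP 3.2).
- **Per-protocol set.** SAP 5 first defines PP as ITT subjects "who do not incur a major protocol violation that would challenge the validity of their data". It then defines "a PP Stage 1 population (subjects from ITT without any major protocol deviation", with no limit to deviations that occur in Stage 1. SAP 7.2 decides PP exclusion subject by subject.

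**The concern.** A sensitivity analysis tests an assumption only if it changes that assumption. Here the subset analyses and the reweighting keep the same likelihood. If they agree with the primary result, the report could say that the MMRM assumptions had been tested when they had not.

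Two assumptions matter. The first is missing at random. If dropouts depart from it differently by arm, or equally but with unequal dropout rates, the estimate is biased, and the bias can go either way. The second is a common covariance under 4:1:1 allocation. If the active arms are more or less variable than placebo, the standard error is wrong in the unbalanced comparison.

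The PP wording raises a different problem. Conditioning the Stage 1 comparison on events after Week 4 discards valid data and makes the Stage 1 set depend on what happened later. Stage 2 treatment differs by Stage 1 arm: everyone on active drug moves to placebo, while 4/7 of re-randomized placebo subjects move to active drug. Later deviations could therefore differ by Stage 1 arm.

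**Working it through.** **What each planned CAPS-5 analysis changes**

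| Analysis | What changes | Missing at random kept? | Common covariance kept? |
|---|---|---|---|
| PP, mITT (8.1.2) | analysis set | yes | yes |
| 0.5/0.5 weights (8.1.2) | how the stage estimates are combined | yes | yes |
| COVID-19 model (10.2) | one added covariate | yes | yes |
| Other structures (8.1.1) | covariance form, only on non-convergence | yes | yes, as written |

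**The plan's own figure.** n = 156 for about 80% power cannot be reproduced, because the effect size, SD and placebo non-responder share are not given. Stage 1 completers are 104 × 0.85 = 88.4 on placebo and 26 × 0.85 = 22.1 per active arm. With an assumed 70% non-responders, Stage 2 completers are 88.4 × 0.7 × 3/7 × 0.89 = 23.6 and 88.4 × 0.7 × 2/7 × 0.89 = 15.7. Then SE = √[0.36(1/88.4 + 1/22.1) + 0.16(1/23.6 + 1/15.7)] = 0.193 SD. The effect that gives 80% power is 2.123 × 0.193 = 0.41 SD. Across assumed shares of 50% to 80% it runs from 0.446 to 0.398 SD.

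**Amount of missing data.** Planned retention through both stages is 0.85 × 0.89 = 75.7%, so about 38 of 156 would not complete both.

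**Shift illustration.** Inputs from the SAP are dropout 15%/11%, weights 0.6/0.4, one-sided alpha 0.10 and power 80%. Assumptions are equal stage effects, the planning dropout rates in every arm, and a fixed SE (a simulation of shifted imputation moved it by about 1% or less). Let m be how much worse dropouts are than missing at random predicts, in multiples of the effect.

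- D = 0.6 × 0.15 + 0.4 × 0.11 = 0.134, if no dropout has endpoint data.
- Factor f = 1 − D(m_active − m_placebo).
- Expected Z = 1.2816 + 0.8416 = 2.1232. Shifted power = Φ(2.1232f − 1.2816).
- Largest p that survives the shift = 1 − Φ(1.2816/f).

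| Scenario | D | f | Power | p limit |
|---|---|---|---|---|
| active 1, placebo 0 | 0.134 | 0.866 | 71% | 0.070 |
| same, half of dropouts with a usable Early Termination CAPS-5 (assumed) | 0.067 | 0.933 | 76% | 0.085 |
| equal shifts, equal dropout | 0.134 | 1.000 | 80% | 0.100 |
| active 0, placebo 1 | 0.134 | 1.134 | 87% | 0.129 |

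Equal shifts cancel only at equal dropout. Suppose active dropout is 20%/14% and the overall rates are held. Placebo dropout is then (0.15 − 0.20 × 2/6)/(4/6) = 12.5% and (0.11 − 0.14 × 4/7)/(3/7) = 7%. An equal shift of 1 gives f = 1 − (0.6 × 0.075 + 0.4 × 0.07) = 0.927.

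**Tipping difference**, (1 − 1.2816/z_p)/0.134: about 1.0, 1.6 and 2.4 times the effect for p = 0.07, 0.05 and 0.03.

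**Common covariance.** Assume the SD in both active arms is 1.25 times placebo.

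- Stage 1 pooled variance = (88.4 + 44.2 × 1.5625)/132.6 = 1.1875.
- Model variance of the contrast = 1.1875(1/88.4 + 1/22.1) = 0.0672.
- True variance = 1/88.4 + 1.5625/22.1 = 0.0820.
- Actual Stage 1 alpha = 1 − Φ(1.2816√(0.0672/0.0820)) = 0.123.
- With 27/18/18 assumed in Stage 2 before 11% dropout, the same steps and the 0.6/0.4 weights give about 0.113 combined.

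**PP Stage 1.** If a share q of Stage 1 subjects, spread evenly over arms, had a major deviation in Stage 2 only (assumed), the SE rises by 1/√(1 − q) − 1. This is 2.6%, 5.4% and 11.8% for q = 5%, 10% and 20%.

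**The case against.** The strongest reply is that this is an exploratory proof-of-concept trial at one-sided 0.10. Protocol 14.4.2 promises no particular missing-data analysis, and the firm defect in 8.1.2 is one overclaiming phrase. That stands, and it is why deleting the phrase is an acceptable minimum.

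Other parts of the reply limit what may be concluded:

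- A reader might infer that missing at random is the only substantive assumption left, because two post-baseline visits per stage need just 3 covariance parameters. The pseudo-code does not support this: the matrix is shared across unequally sized arms, which is itself an assumption.
- A reader might infer that 8.1.2 claims to test missing data. It names no assumption, so the point is that none is tested.
- A reader might infer that no such analysis exists anywhere. A figure mark stands directly before the 8.1.2 list, and the subsections of 8.3 before 8.3.5 are not visible. SAP 6.1.3 makes a hidden imputation analysis unlikely but cannot exclude it.
- A reader might take 0.866, 71% and 0.070 as the expected effect. CAPS-5 is collected at Early Termination, so some dropouts may have usable values. How these are assigned to a visit is not stated in the available Section 6.
- A reader might infer that Stage 2 deviations differ by Stage 1 arm. Treatment differs by design, but the documents do not show that deviations do. The general PP sentence refers to validity, and the pre-lock review in SAP 7.2 could limit exclusions by stage, though nothing says it will.

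**Conclusion.** Both parts hold as points the sponsor should correct. Neither undermines the primary analysis itself.

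The text available contains no CAPS-5 analysis that relaxes missing at random or the common covariance, so the purpose stated in 8.1.2 is not met. The possible effect is modest and can run in either direction. The 71% case is near the upper bound for its scenario, and it becomes 76% if half of dropouts supply a usable final CAPS-5. Results with p well below 0.05 would need a between-arm difference in shift of more than about 1.6 times the whole treatment effect to change the conclusion. These sizes rest on the planning dropout rates, equal stage effects and a fixed SE. The alpha figures rest on an assumed SD ratio.

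The PP Stage 1 definition, read literally, discards valid Stage 1 data. Its cost in precision depends on a deviation rate that the documents do not give, and it affects only a sensitivity set.

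**What to change.** 1. **Add to SAP 8.1.2** a delta-adjusted multiple-imputation analysis of CAPS-5 within each stage.
   - Include all subjects randomized to that stage's analysis arms, also those with no post-baseline CAPS-5.
   - Vary the shift separately in active and placebo arms over a prespecified grid in CAPS-5 points, and report the full grid whether or not the primary result is significant.
   - Combine stages with the same 0.6/0.4 Z, and give the tipping difference for each dose where one exists.
2. **Amend SAP 6.1.3** so that its exclusion of further imputation excepts this analysis. Otherwise the two sections would conflict. State there how an Early Termination CAPS-5 is assigned to a visit.
3. **Optionally** refit the MMRM with arm-specific covariance.
4. **If none of this is adopted,** delete the closing words of the 8.1.2 sentence on testing the MMRM assumptions.
5. **Define PP by stage:** a major deviation that challenges data validity excludes data from the stage in which it occurs and any later stage, not from an earlier one.

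The cost is SAP wording and modest extra programming before unblinding. A borderline result may be shown to be fragile. No protocol amendment is needed, since Protocol 14.4.2 and 14.4.3 leave these analyses and populations to the SAP.

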## 8.2. Secondary Efficacy Analysis

PCL-5 total score, PSQI score, PSQI-A score, BAC symbol coding, CGI-S scale, HADS-A scale, and HADS-D scale, will be analyzed based on the methods described in Section 8.1.1, using the endpoint appropriate baseline covariate.

## 8.3. Exploratory Efficacy Analyses

### 8.3.5. Subgroup Analyses

The primary efficacy endpoint will be described on the following subgroups

1. Gender
2. Race (White, Non-white)
3. Time Since Trauma ( $\leq$  median and  $>$  median), date of trauma from medical

history where mhterm equals PTSD, POST TRAUMATIC STRESS DISORDER

4. Marital Status (Married, Not Married)
5. Trauma type(Sexual Abuse (from medical history where preferred term in “Sexual Abuse”, “Victim of Sexual Abuse) vs. other)
6. Taken Pain Medication during study () at any point in the study (Yes, No). The list of concomitant medications will be reviewed prior to database lock and pain medications of interest will be identified for this analysis.
7. PSQI Sleeping Status (Good Sleeper total score <=5, Poor Sleeper total score >5) at baseline (Day 1 only)
8. HADS-A and HADS-D Score categories (normal (0-7), borderline abnormal (8-10) and abnormal (>=11))
9. Subjects with and without AEs of interest at any point during the study (Yes, No)
10. Subjects with high avoidance scores- Subjects with score 3,4 in avoidance categories of CAPS5 Q6,7 or distant from other people, Q13.

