**14.4.1.1. Primary Efficacy Endpoint Analysis**

The ITT population will be the primary efficacy analysis population. The data from the NYX-783 treatment groups (using both Stage 1 and Stage 2) will be used for the comparison to placebo. This consists of subjects (randomized to placebo and NYX-783 from treatment arms [1], [2] and [3] for Stage 1 and treatment arms [7], [8], and [9] for Stage 2.

The primary efficacy endpoint will be evaluated using the weighted combination of the estimated treatment effects from the stage-specific mixed models for repeated measures (MMRM). The MMRM models will include variables for treatment group, visit, treatment-by-visit interaction term, baseline CAPS-5 score and baseline-by-visit interaction. An unstructured covariance matrix will be used. In the case of non-convergence, alternative covariance structures will be used. The sequence of alternative covariance structures will be specified in the SAP. The Kenward-Roger approximation will be used to adjust the denominator degrees of freedom. The treatment effect will be assessed as the differences in least-squares mean (LS mean) changes from baseline to Week 4 (Stage 1) and from Week 4 to Week 8 (Stage 2) for the NYX-783 50 mg QD, NYX-783 10 mg QD, and placebo groups, pooled across Stages 1 and 2 using prespecified 0.6/0.4 weighting for Stage 1/Stage 2.

Subgroup analyses will be conducted with visit, treatment, investigator, treatment-by-visit interaction, the corresponding baseline score, and the baseline-by-visit interaction – and, if applicable – the corresponding change from screening to baseline will be included in the model.

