## 9.2. Adverse Events of Interest

The following are AEs of interest.

- Suicidality (ideation or attempt)
- Abuse and/or dependency events (drug & alcohol)
- Dissociative experience events
- Depression (or worsening depression)

The following AEs are also of potential clinical interest

- Eating disorder
- Nightmares (or worsening nightmares)
- Anxiety (or worsening anxiety)
- Panic attack
- Self-injurious behavior
- Aggressive behavior toward others
- Negative social events (e.g. loss of job, separation from significant other)

A summary of incidence rates (frequencies and percentages) by SOC, and preferred term will be prepared for all adverse event of interest listed above. The summary will be presented for each Stage as described in Section 9.1.

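### Two exploratory efficacy subgroups (SAP 8.3.5, items 6 and 9) are defined by events after randomisation, under one flag spanning both stages, so arm differences within them can be biased in either direction

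*SAP*

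**What the plan says.** SAP 8.3.5 sits under the exploratory efficacy analyses and opens: "The primary efficacy endpoint will be described on the following subgroups". Ten subgroups follow. Item 6 is pain medication taken "at any point in the study (Yes, No"), with the list of relevant drugs to be settled before database lock. Item 9 is "Subjects with and without AEs of interest at any point during the study (Yes, No"). Item 7, between them, is tied to a time before treatment: "Poor Sleeper total score >5) at baseline (Day 1 only").

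SAP 9.2 has two lists. The first, AEs of interest, covers suicidality, abuse or dependency, dissociative events and "Depression (or worsening depression"). The second, of potential clinical interest, adds among others anxiety and "Nightmares (or worsening nightmares"). Item 9 does not say whether it uses one list or both.

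The visible SAP text names no subgroup test or interaction, and does not caution that items 6 and 9 are not randomised comparisons. Protocol 14.4.1.1 goes further than description: "Subgroup analyses will be conducted with visit, treatment, investigator, treatment-by-visit interaction, the corresponding baseline score". A model with those terms yields treatment contrasts.

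Under SAP 3.5, subjects on active drug in Stage 1 receive placebo in Stage 2, and Stage 1 placebo subjects are re-randomised 3:2:2 to placebo, 50 mg or 10 mg.

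**The concern.** Randomisation makes arms comparable within groups fixed before treatment. It gives no such protection within groups formed by something that treatment may change. If the event is also linked to outcome, splitting on it selects differently in each arm, and a difference can appear where the drug has no effect on CAPS-5.

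Both links are plausible for item 9. Depression, and nightmares if the second list counts, lie close to CAPS-5 content. Protocol 12.5.3 asks sites to look for emerging dissociative symptoms, a type of event that the drug might affect.

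The any-time flag adds a problem specific to this design. An event at Week 6, often on a different treatment, decides which subgroup a subject joins for the Stage 1 comparison.

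At stake is interpretation. SAP section 1 allows planned analyses to enter study reports, submissions and manuscripts, where a gap between subgroups could be read as effect modification.

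**Working it through.** The plan gives no figure for this point, and no event rate or link between AEs and CAPS-5. Those values below are assumptions. Bias is active minus placebo in SD of CAPS-5 change, with the true effect set to zero. Negative favours the drug.

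**Scale.** The stated power of about 80% cannot be reproduced, because no effect size or SD is given. For reference, the variance in SD units is 0.6²(1/88.4 + 1/22.1) + 0.4²(1/n₇ + 1/n₈). The first two sizes are 104 and 26 (4:1:1 of 156) after 15% dropout. If 60% of placebo completers are non-responders (assumed), 11% dropout and the 3:2 ratio give n₇ = 20.2 and n₈ = 13.5. The SE is then 0.200, and 80% power at one-sided 0.10 needs (1.282 + 0.842) × 0.200 = 0.43 SD. Non-responder shares of 50% to 80% give 0.45 to 0.40 SD.

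**One stage.** Let e be worsening in SD units and logit P(AE) = −1.7 + 0.8e + ln(OR) × active. The placebo AE rate is about 18%.

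**Two stages, any-time flag.** The same model applies in each stage. Stage 1 active subjects go to placebo and 4/7 of Stage 1 placebo subjects go to active. The subgroup is an AE in either stage and the contrast is the Stage 1 outcome. Dropout is ignored.

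| Model (log-odds 0.8 per SD) | OR | Bias, AE yes | Bias, AE no |
|---|---|---|---|
| One stage | 1 | 0 | 0 |
| One stage | 2 | −0.09 | −0.08 |
| One stage | 3 | −0.15 | −0.13 |
| One stage | 0.5 | +0.08 | +0.05 |
| Two stages, independent, intercept −2.2 | 2 | +0.10 | −0.06 |
| Two stages, independent, intercept −2.2 | 3 | +0.14 | −0.10 |
| Two stages, independent, intercept −1.7 | 2 | +0.07 | −0.08 |
| Two stages, independent, intercept −1.7 | 3 | +0.09 | −0.13 |
| Two stages, correlation 0.5, intercept −1.7 | 2 | +0.03 | −0.05 |
| Two stages, correlation 0.5, intercept −1.7 | 3 | +0.03 | −0.10 |

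The sign changes in the AE-yes group for a reason. Flagged Stage 1 active subjects were more often flagged by a Stage 1 event, which selects a worse Stage 1 outcome. Flagged Stage 1 placebo subjects were more often flagged in Stage 2, which says less about Stage 1. So the two subgroups can point in opposite directions with no drug effect at all.

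**Second model, one stage.** A latent normal event variable has correlation ρ with worsening. The bias is ρ[f(p_active) − f(p_placebo)], where f(p) = φ(z)/p for AE yes, −φ(z)/(1 − p) for AE no, and z is the upper-p normal quantile. With 20% on placebo, 40% on active and ρ = 0.5:
- AE yes: 0.5 × (0.966 − 1.400) = −0.22
- AE no: 0.5 × (−0.644 + 0.350) = −0.15

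With 104 against 26 subjects, a one-sided t-test at 0.10 (which the SAP does not name) would then show a false benefit 26% and 23% of the time. With 30% on active and ρ = 0.3 the rates are 14% and 13%. Equal event rates, or ρ = 0, give no bias. With 10% on active and ρ = 0.5 the bias is +0.18 and +0.08, against the drug.

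**The case against.** A reader might infer that these comparisons are biased, and in the drug's favour. The documents do not support that. Bias needs the drug to change the event rate and the event to track outcome, and the first is not shown. The Phase 1 study in protocol section 5 reports only two mild, possibly related events, headache and fatigue, neither on the SAP 9.2 lists. The direction can also go either way.

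Other points stand in part:
- **Recording rule.** Protocol 12.5.3 keeps symptoms of lack of efficacy out of the AE record unless there is a clinically significant safety concern. This weakens the link between AEs and CAPS-5 without removing it.
- **AE lists.** Anxiety and nightmares are in the second list, so their inclusion in item 9 is uncertain.
- **Dilution by switching.** With AE risks per stage of 10% on placebo and 25% on drug (odds ratio 3), the any-time risk is 1 − 0.75 × 0.90 = 32.5% for Stage 1 active. For Stage 1 placebo it is 1 − 0.90 × (1 − 0.186) = 26.7%, where 0.186 = 4/7 × 0.25 + 3/7 × 0.10. The odds ratio falls to about 1.3. But the two-stage results show that bias remains, with a changed sign among subjects with AEs.
- **Pain medication.** SAP 9.7 counts drugs started before the first dose and continued as concomitant too, so item 6 is partly a baseline trait. It was not modelled.
- **Consequence.** The displays are exploratory and the SAP's verb is to describe. At one-stage rates for an odds ratio of 2 (18% and 29%), the AE-yes group would hold about 19 placebo and 8 active subjects. The SE is √(1/19 + 1/8) ≈ 0.42 SD, well above the bias. That limits the harm, but noise does not make a comparison valid, and arm means shown side by side carry the same selection without a p-value.

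**Conclusion.** The concern holds in limited form. Items 6 and 9 use post-randomisation information, and the single flag ignores the Week 4 change of treatment. Arm differences within them can be biased in either direction, and can differ between subgroups with no true effect modification.

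For item 9, the tabulated scenarios with AE odds ratios of 2 to 3 give a Stage 1 bias of roughly 0.03 to 0.15 SD, at most about a third of the 0.40 to 0.45 SD reference. This rests on the assumed odds ratios, event rates, log-odds and correlation between stages. The second model reaches 0.22 SD at its strongest setting shown, so the range is illustrative and not a bound. No magnitude is shown for item 6.

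A reader might also infer a threat to the primary result. There is none: the primary test and its alpha do not use these subgroups. The change is worth making because the plan as written leads to unprotected arm comparisons and the remedy is small.

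**What to change.** - **Item 6:** define it as pain medication in use at Day 1, meaning started before and still ongoing at the first dose.
- **Item 9:** remove it from the efficacy subgroups and leave these events to the safety tables already planned in SAP 9.2. If the sponsor keeps it, show it by stage, give no between-arm efficacy contrast, state that it is not a randomised comparison, and say which SAP 9.2 list defines it.

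The cost is a few lines of SAP text. Medication use before and after the first dose is already collected (protocol 10.4, SAP 9.7), and power and conduct do not change. The downside is that one exploratory display is redefined, so it no longer reflects pain medication started during the study, and one is dropped or restricted.
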